8.4.6 Physical Examination

PE findings will be presented as a data listing only.

9 INTERIM AND DMC ANALYSES

9.1 Interim Analysis

No formal interim analysis is planned.

9.2 DMC Analysis

An independent data monitoring committee (IDMC) will be formed before study initiation. The IDMC's objectives and operational details will be defined in a separate document (IDMC Charter) which will be finalized before the first subject is screened in the study. The IDMC will conduct regular planned safety reviews of study data as outlined in the IDMC Charter.

Analyses for IDMC purposes are described in a separate IDMC SAP.

10 LIST OF APPENDICES

10.1 Appendix A: Schedule of Assessments

Table 10-1 Study VX15-661-112: Screening

Event/Assessment	Screening Period (Day -28 through Day -1)
Informed consent (and assent, when applicable)	X
Demographics	X
Medical history	X
Ophthalmological history	X
CF genotype ^a	X
FSH ^b	X
Serum pregnancy test (all females of childbearing potential) ^c	X
Hematology	X
Coagulation	X
Serum chemistry	X
Urinalysis	X
Weight and height ^d	X
Ophthalmologic examination ^e	X
Complete physical examination	X
Vital signs ^f	X
Pulse oximetry ^f	X
Standard 12-lead ECG ^g	X
Spirometry ^h	X
Inclusion/exclusion criteria review	X
Prior and concomitant medications	X
Sweat chloride ⁱ	X
AEs and SAEs	Continuous from signing of the ICF and assent (where applicable) through the Safety Follow-up Visit

AE: adverse event; CF: cystic fibrosis; ECG: electrocardiogram; FSH: follicle-stimulating hormone; ICF: informed consent form; SAE: serious adverse event.

- ^a All subjects will be tested for CF genotype. Specific instructions will be provided in the Laboratory Manual. CF genotyping may be waived if the subject has a documented result from a previous Vertex study.
- ^b FSH will be measured for any suspected postmenopausal female with at least 12 months of continuous spontaneous amenorrhea. Serum FSH levels must be ≥ 40 mIU/mL to be considered postmenopausal.
- ^c Any female subject who does not meet the criteria for non-childbearing potential is considered to be of childbearing potential and must have a serum pregnancy test.
- ^d Weight and height will be measured with shoes off.
- ^e An ophthalmologic examination will be conducted on subjects of all ages by an ophthalmologist. The ophthalmologic examination does not need to be repeated if there is documentation of an examination that met the protocol criteria and was conducted within 3 months before the start of the Screening Period or if there is documentation of bilateral lens removal (Section 11.6.8 of Clinical Study Protocol).
- ^f Vital signs and pulse oximetry will be collected after the subject has been at rest (seated or supine) for 5 minutes.
- ^g A standard 12-lead ECG will be performed after the subject has been supine for at least 5 minutes.
- ^h Spirometry may be performed pre- or postbronchodilator (Section 11.5.2).
- ⁱ A sweat chloride test must be performed at the Screening Visit if an eligible sweat chloride value is not available in the subject's medical records and the Screening Visit value is needed to establish eligibility. For subjects using sweat chloride values documented in their medical records to establish eligibility, the sweat chloride test at the Screening Visit is optional.

Table 10-2 Study VX15-661-112: Treatment Period (Day 1 to Week 72), Early Termination of Treatment Visit, and Safety Follow-up Visit Assessments

Event/Assessment ^a	Day 1	Day 15 (± 3 days)	Week 4, Week 12, (± 1 week)	Week 24 (± 1 week)	Week 36, Week 48, Week 60 (± 1 week)	Week 72 (± 1 week)	Early Termination of Treatment Visit (Within 7 days After Last Dose of Study Drug)	Safety Follow-up Visit 4 weeks (± 7 days) After Last Dose of Study Drug ^b
Clinic visit	X	X	X	X	X	X	X	X
Inclusion and exclusion criteria review ^c	X							
Randomization ^d	X							
Complete physical examination ^f	X					X	X	X
Pregnancy test ^g	urine		urine	urine	urine	urine	serum	serum

^a All assessments will be performed before dosing unless noted otherwise. If study drug is not administered on the day of the visit (i.e., study drug interruption or premature discontinuation of study drug treatment), only 1 set of assessments will be collected.

^b The Safety Follow-up Visit is not required for subjects who complete the Week 72 Visit and have enrolled in the TEZ/IVA open-label extension study, VX14-661-110, within 28 days after the last dose of study drug.

^c The screening inclusion and exclusion criteria should be re-reviewed before administration of study drug on Day 1.

^d Randomization must occur after the informed consent/assent has been obtained and all inclusion and exclusion criteria are met and before the first dose of study drug. Randomization will be done through an interactive web response system. Randomization may occur on Day -1 if the above conditions for randomization have been met.

^f In addition to the indicated visits, a symptom-targeted physical examinations will occur at any time during the study if triggered by adverse events (AEs) or if deemed necessary by the investigator.

^g Pregnancy tests will be performed for all female subjects of childbearing potential. Day 1 results will be reviewed before dosing and the Low-dose CT scan. Week 72 results will be reviewed before the Low-dose CT scan.

Table 10-2 Study VX15-661-112: Treatment Period (Day 1 to Week 72), Early Termination of Treatment Visit, and Safety Follow-up Visit Assessments

Event/Assessment ^a	Day 1	Day 15 (± 3 days)	Week 4, Week 12, (± 1 week)	Week 24 (± 1 week)	Week 36, Week 48, Week 60 (± 1 week)	Week 72 (± 1 week)	Early Termination of Treatment Visit (Within 7 days After Last Dose of Study Drug)	Safety Follow-up Visit 4 weeks (± 7 days) After Last Dose of Study Drug ^b
Low-dose CT scan ^h	X					X		
Standard digital ECG ^m	X	X	X	X	X	X	X	X
Vital signs ⁿ	X	X	X	X	X	X	X	X
Pulse oximetry ⁿ	X	X	X	X	X	X	X	X

^h Low-dose CT scans [REDACTED] should be performed on the same day. If not possible for logistical reasons, Low-dose CT scans [REDACTED] should be performed within ± 4 days of the scheduled visit. Day 1 assessments must be completed before dosing. The Week 72 CT scan may be delayed for up to 60 days if the subject is recovering from a pulmonary exacerbation. The medical monitor should be notified about the extension. The scan should be done after the pulmonary exacerbation is resolved and at least 28 days after the antibiotic regimen for the treatment of pulmonary infection has been completed. If this antibiotic regimen is not completed by the end of the 60-day extension, the subject may complete the CT scan within the first 30 days of enrolling in Study VX14-661-110; or within 1 week of [REDACTED]

^m All standard 12-lead ECGs will be performed before dosing and after the subject has been supine for at least 5 minutes. The predose ECGs collected at the Day 1 Visit will be performed in triplicate.

ⁿ Vital signs and pulse oximetry will be collected before dosing and after the subject has been at rest (seated or supine) for at least 5 minutes. In addition to the indicated visits, symptom-targeted vital signs will occur at any time during the study if triggered by AEs or if deemed necessary by the investigator.

Table 10-2 Study VX15-661-112: Treatment Period (Day 1 to Week 72), Early Termination of Treatment Visit, and Safety Follow-up Visit Assessments

Event/Assessment ^a	Day 1	Day 15 (± 3 days)	Week 4, Week 12, (± 1 week)	Week 24 (± 1 week)	Week 36, Week 48, Week 60 (± 1 week)	Week 72 (± 1 week)	Early Termination of Treatment Visit (Within 7 days After Last Dose of Study Drug)	Safety Follow-up Visit 4 weeks (± 7 days) After Last Dose of Study Drug ^b
Hematology	X			X	Wk 48 only	X	X	X
Lipid and vitamin levels	X			X	Wk 48 only	X	X	X
Coagulation	X					X		X
Serum chemistry ^p	X	X	X	LFT only	LFT only	X	X	X
Urinalysis	X					X		X
Study drug count		X	X	X	X	X		
Meal(s) or snack(s) at site ^q	X	X	X	X	X			

CT: computed tomography; ECG: electrocardiogram; LFT: liver function test;

^p Blood samples will be collected before the dose of study drug. At Weeks 24, 36, 48, and 60, only samples for LFT analysis will be collected.

^q Food will be provided after all predose assessments have occurred.

Table 10-2 Study VX15-661-112: Treatment Period (Day 1 to Week 72), Early Termination of Treatment Visit, and Safety Follow-up Visit Assessments

Event/Assessment ^a	Day 1	Day 15 (± 3 days)	Week 4, Week 12, (± 1 week)	Week 24 (± 1 week)	Week 36, Week 48, Week 60 (± 1 week)	Week 72 (± 1 week)	Early Termination of Treatment Visit (Within 7 days After Last Dose of Study Drug)	Safety Follow-up Visit 4 weeks (± 7 days) After Last Dose of Study Drug ^b	
Study drug dosing ^f	Day 1 through Week 72								
Ophthalmologic examination						X ^s	X ^t	X ^t	
Concomitant medications	X	X	X	X	X	X	X	X	
Concomitant treatments and procedures	X	X	X	X	X	X	X	X	
Adverse events and serious adverse events	Continuous from signing of the informed consent form and assent (where applicable) through the Safety Follow-up Visit								

^f Subjects will take study drug as specified in Section 10.2. On days of scheduled visits, the subject’s dose of study drug will be administered at the site after predose assessments have been completed. Study drug administration should be completed within 5 minutes. At the Week 72 Visit, the morning dose of study drug will NOT be administered. The last dose of study drug will be the evening dose administered the day before the Week 72 Visit. If the Week 72 CT scan is delayed to allow a subject to recover from [REDACTED], study drug will continue for up to 60 days until the Week 72 CT scan has been completed or the subject has enrolled in Study VX14-661-110; for these subjects, the last dose of study drug will be the evening dose administered the day before the CT scan or before the Day 1 Visit of Study VX14-661-110.

^s All subjects <18 years of age at the Screening Visit will have an ophthalmologic examination conducted by a licensed ophthalmologist at Week 72. This exam may be completed within 4 weeks before the Week 72 Visit, but must be completed by the end of the Week 72 Visit.

^t Subjects <18 years of age at the Screening Visit who discontinue treatment after receiving at least 1 dose of study drug will have an ophthalmologic examination performed by a licensed ophthalmologist at the Safety Follow-up or the Early Termination of Treatment Visit. This examination may be completed at either the Early Termination of Treatment or Safety Follow-up Visit, but must be completed by the end of the Safety Follow-up Visit.

10.2 Appendix B: Analysis Visit Window Mapping Rules for Efficacy and Safety Measurements

Table 10-3 Visit Window Mapping Rules

Assessments	Visit	Target Study Day	Visit Window (in study days)
Standard 12-lead ECG Vital signs Pulse oximetry Serum Chemistry	Baseline	1	≤1
	Day 15	15	[2, 22]
	Week 4	29	[23, 57]
	Week 12	85	[58, 127]
	Week 24	169	[128, 211]
	Week 36	253	[212, 295]
	Week 48	337	[296, 379]
	Week 60	421	[380, 463]
	Week 72	505	[464, 519]
	ETT	N/A	Follow the individual visit window to be mapped to individual visits
Safety Follow-up Visit	N/A	Nominal	
Hematology Lipid and Vitamin Levels	Baseline	1	≤1
	Week 24	169	[2, 253]
	Week 48	337	[254, 421]
	Week 72	505	[422, 519]
	ETT	N/A	Follow the individual visit window to be mapped to individual visits
	Safety Follow-up Visit	N/A	Nominal
Coagulation	Baseline	1	≤1
	Week 72	505	[464, 519]
	Safety Follow-up Visit	N/A	Nominal

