11.6.2 Clinical Laboratory Assessments

Blood and urine samples will be analyzed at a central laboratory, except for urine pregnancy tests, which will be analyzed at the site. Fasting is not required at any time point. On Day 1, blood samples will be collected before the first dose of the study drug. At all other scheduled visits, these samples will be collected in the order specified in [Section 11.1](#).

Laboratory test results that are abnormal and considered clinically significant will be reported as AEs (see [Section 13.1](#)).

The safety laboratory test panels are shown in [Table 11-1](#).

Table 11-1 Safety Laboratory Test Panels

Serum Chemistry	Hematology	Urinalysis ^a
Glucose	Hemoglobin	Leukocyte esterase
Blood urea nitrogen	Erythrocytes	Nitrite
Creatinine	Mean corpuscular hemoglobin	Urobilinogen
Sodium	Mean corpuscular hemoglobin concentration	Urine protein
Potassium	Mean corpuscular volume	pH
Calcium	Reticulocytes	Urine blood
Chloride	Platelets	Specific gravity
Magnesium	Leukocytes	Urine ketones
Bicarbonate	Differential (absolute and percent):	Urine bilirubin
Inorganic phosphate	Eosinophils	Urine glucose
Total bilirubin, direct bilirubin	Basophils	
Alkaline phosphatase	Neutrophils	
Aspartate aminotransferase	Lymphocytes	
Alanine aminotransferase	Monocytes	
Lactate dehydrogenase	Coagulation Studies	
Gamma-glutamyl transpeptidase	Activated partial thromboplastin time	
Total protein	Prothrombin time	
Albumin	Prothrombin time	
Creatine kinase	International Normalized Ratio	
Amylase		
Lipase		
Vitamin Levels		
Vitamins A, D, E, K, and B12		
Lipid Panel		
Total cholesterol, triglycerides		
Low-density lipoprotein (LDL)		
High-density lipoprotein (HDL)		

^a If urine is positive for leukocyte esterase, nitrite, protein, or blood, microscopic examination of urine will be performed for leukocytes, erythrocytes, crystals, bacteria, and casts.

Pregnancy (β-human chorionic gonadotropin) Tests for Females of Childbearing Potential: Serum samples will be obtained as specified in [Table 3-1](#) and [Table 3-2](#) and analyzed at the central laboratory. Urine pregnancy test kits will be provided by the central laboratory and performed and analyzed at the site as specified in [Table 3-2](#). The urine pregnancy test may be performed on Day 1 and must be negative before the randomization. Tests must also be reviewed and confirmed as negative before each LDCT scan.

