11.6.3 Liver Function Test Parameters

Liver Function Testing

Liver function testing (ALT, AST, GGT, ALP, direct bilirubin, and total bilirubin) must be performed as noted in [Table 3-2](#) for serum chemistry, while subjects are receiving study drug treatment and at the Safety Follow-up Visit. These blood samples should be processed and shipped immediately per the Laboratory Manual.

Subjects with new treatment-emergent ALT or AST elevations of $>3 \times \text{ULN}$ and clinical symptoms must be followed closely, including repeat confirmatory testing performed by the central laboratory within 48 to 72 hours of the initial finding and subsequent close monitoring of ALT and AST levels, as clinically indicated. In addition, if ALT or AST is $>5 \times \text{ULN}$, repeat follow-up levels must be obtained within 7 ± 2 days.

If a subject cannot return to the site for liver function testing, a local laboratory may be used. Elevations in LFTs at the local laboratory must be reported immediately to the medical monitor, and the subject must have the tests repeated and sent to the central laboratory as soon as possible (ideally within 48 to 72 hours).

Study Drug Interruption

Study drug administration **must be interrupted** immediately (before confirmatory testing), and the medical monitor must be notified, if any of the following criteria is met:

- ALT or AST $>8 \times$ ULN
- ALT or AST $>5 \times$ ULN for more than 2 weeks
- ALT or AST $>3 \times$ ULN, in association with total bilirubin $>2 \times$ ULN and/or clinical jaundice

A thorough investigation of potential causes should be conducted and the subject should be followed closely for clinical progression.

If no convincing alternative etiology (e.g., acetaminophen use, viral hepatitis, or alcohol ingestion) for the elevated transaminases is identified, regardless of whether ALT or AST levels have improved, study drug treatment must be permanently discontinued if repeat testing within 48 to 72 hours confirms the initial elevation. Subjects in whom treatment is discontinued for elevated transaminases should have their transaminases monitored closely until levels normalize or return to baseline.

Resumption of Study Drug

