8 STATISTICAL ANALYSIS

8.1 General Considerations

The Schedule of Assessments is provided in [Appendix A \(Section 10.1\)](#).

All individual subject data for those randomized or exposed to study drug will be presented in data listings.

Continuous variables will be summarized using the following descriptive summary statistics: the number of subjects (n), mean, standard deviation (SD), standard error (SE), median, minimum value (min), and maximum value (max).

Categorical variables will be summarized using counts and percentages.

Baseline Value, unless otherwise specified, is defined as the most recent non-missing measurement (scheduled or unscheduled) collected prior to the first dose of study drug. For ECGs, the baseline will be defined as the average of the 3 pretreatment measurements (triplicate) on Day 1.

Absolute Change from baseline will be calculated as Postbaseline value - Baseline value.

Relative change from baseline will be calculated and expressed in percentage as $100\% \times (\text{Postbaseline value} - \text{Baseline value}) / \text{Baseline value}$.

Treatment Emergent (TE) Period will include the time from the first dose to Safety Follow-up Visit. For subjects who do not have a Safety Follow-up Visit because they rolled over into the open-label extension study within 28 days after the last dose of study drug, the end of the TE period will be the date of rollover into the extension study. For subjects who do not have a Safety Follow-up Visit and did not roll over into the extension study, the end of the TE period will be 28 days after the date of last dose. The TE period will be used for safety analyses unless otherwise specified.

Unscheduled Visits: Unscheduled visit measurements will be included in the analysis as follows:

- In scheduled visit windows per specified visit windowing rules;
- In the derivation of baseline and last on-treatment measurements;
- In the derivation of maximum/minimum on-treatment values and maximum/minimum changes from baseline values for safety analyses;
- In individual subject data listings where appropriate.

Visit Windowing Rules: The analysis visit windows for protocol-defined visits are provided in [Appendix B \(Section 10.2\)](#). The windows will be applied using the following rules for both scheduled and unscheduled visits:

1. If no measurement is available within a visit window, the assessment will be considered missing for the visit;

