8.4.2 Clinical Laboratory

For the treatment emergent laboratory measurements, the raw values and change from baseline values of the continuous hematology and chemistry results will be summarized in SI units by treatment group at each scheduled time point. For hematology and chemistry, the number and percentage of subjects with abnormal low (<LLN) value and with abnormal high (>ULN) value at each scheduled time point will be summarized.

For LFT and CPK results (alanine aminotransferase [ALT], aspartate aminotransferase [AST], serum alkaline phosphatase [ALP], total bilirubin and CPK), the following additional analyses will be conducted:

- The number and percentage of subjects who meet the thresholds for LFT and CPK according to the criteria defined in [Appendix H \(Section 10.8\)](#) will be summarized by visit and during the TE period. The shift of the threshold criteria from baseline to post baseline will be summarized.
- For each LFT, the box plot of LFT value/ULN will be provided against visit.
- A scatter plot of maximum values of ALT versus maximum values of total bilirubin will also be presented. Note that the ALT and Total bilirubin values are presented on a logarithmic scale. The graph will be divided into 4 quadrants with a vertical line corresponding to 3xULN for ALT and a horizontal line corresponding to 2xULN for total bilirubin. A similar graph of maximum values of AST versus maximum values of total bilirubin will be presented as well.
- A listing of subjects with elevated LFT results during the TE period will be presented. For each subject in the listing, LFT assessments at all visits will be included.

Results of GI/Nutrition laboratory parameters (specified in SAP M2) will be summarized and subject data listings will be provided. The number and percentage of subjects with abnormal low (<LLN) value and with abnormal high (>ULN) value at each scheduled time point will be summarized for GI/nutritional parameter and listed separately. In addition, boxplots by visit will be provided for GI/Nutrition laboratory parameters.

Results of serum pregnancy test, urinalysis, and the urine/serum pregnancy test will be listed in individual subject data listings only.

In addition, a listing containing individual subject hematology, chemistry, and coagulation values outside the reference ranges will be provided. These listings will include data from scheduled and unscheduled time points.

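### SAP Table 10-3 gives all serum chemistry windows at Weeks 24 to 60, where only liver function tests are drawn, so by-visit rows there for CPK and other non-LFT analytes could hold only early-termination and unscheduled samples

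*SAP*

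**What the plan says.** **Windows.** SAP Appendix B, Table 10-3 has one block headed "Standard 12-lead ECG Vital signs Pulse oximetry Serum Chemistry". After baseline its visits are Day 15 and Weeks 4, 12, 24, 36, 48, 60 and 72. Early-termination (ETT) results are handled by the entry "Follow the individual visit window to be mapped to individual visits". SAP 8.1 also places unscheduled results "In scheduled visit windows per specified visit windowing rules". For safety parameters it keeps the Safety Follow-up Visit under its nominal label.

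**Sampling.** In SAP Appendix A, Table 10-2, the row "Serum chemistry ^p" is marked for the full panel at Day 1, Day 15, Weeks 4, 12 and 72, ETT and Safety Follow-up. The remaining visits are marked for LFTs alone, and the footnote reads "At Weeks 24, 36, 48, and 60, only samples for LFT analysis will be collected". Protocol Table 3-2 agrees.

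**Analytes.** Protocol 11.6.3 defines the LFT panel: "Liver function testing (ALT, AST, GGT, ALP, direct bilirubin, and total bilirubin) must be performed as noted in" the schedule. Protocol Table 11-1 lists "Creatine kinase" (CPK), creatinine, glucose, electrolytes, amylase and lipase under serum chemistry. None of these is in the LFT panel.

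**Outputs.** SAP 8.4.2 summarizes continuous chemistry, with counts below and above the normal range, at the scheduled time points. It adds threshold counts for LFTs and CPK that "will be summarized by visit and during the TE period".

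**The concern.** Table 10-3 names four analysis visits for all serum chemistry at which most of the panel is never scheduled. If the table is programmed as written, a CPK or creatinine row for Week 48 contains no subject who is simply continuing on treatment. It contains subjects who stopped near that day and subjects who had an extra blood draw for some reason. Such a row sits in the same table as Week 12 and Week 72 rows built from nearly everyone, and a reader scanning down the visits would be comparing different populations. Between arms, the comparison would depend on who stopped and why.

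The rest of the table suggests an oversight. Hematology with lipids and vitamins has its own block at Weeks 24, 48 and 72, and coagulation has its own at Week 72. Both match their sampling schedules. Non-LFT chemistry is the exception.

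**Working it through.** **1. Reproduce the plan's windows.** Target day = 7 × week + 1, with Day 15 as given: 15, 29, 85, 169, 253, 337, 421, 505. Each upper bound is the midpoint of adjacent targets:

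- (15 + 29)/2 = 22
- (29 + 85)/2 = 57
- (85 + 169)/2 = 127
- (169 + 253)/2 = 211
- (253 + 337)/2 = 295
- (337 + 421)/2 = 379
- (421 + 505)/2 = 463
- last bound: 505 + 14 = 519

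These give [2, 22], [23, 57], [58, 127], [128, 211], [212, 295], [296, 379], [380, 463] and [464, 519], exactly as in Table 10-3. The same rule on Days 169, 337 and 505 returns the hematology windows [2, 253], [254, 421] and [422, 519].

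**2. Where scheduled full panels can fall.** Using the tolerances in the Schedule of Assessments:

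| Full-panel visit | Target ± tolerance | Days |
|---|---|---|
| Day 15 | 15 ± 3 | 12–18 |
| Week 4 | 29 ± 7 | 22–36 |
| Week 12 | 85 ± 7 | 78–92 |
| Week 72 | 505 ± 7 | 498–512 |

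The Week 24 to Week 60 windows together run from Day 128 to Day 463, which is 463 − 128 + 1 = 336 days. No on-time full panel falls in that range. A Week 12 draw would have to be 128 − 85 = 43 days late to reach it, or a Week 72 draw 505 − 463 = 42 days early.

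**3. What can fill those windows for non-LFT analytes.** ETT panels can, because they are full panels and are windowed by study day. Unscheduled draws can, because they are windowed too. Safety Follow-up panels cannot, because they stay nominal. Scheduled Week 24 to Week 60 samples cannot, because they are LFT only.

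**4. How many values.** The documents give no discontinuation rate. As an assumption, take 10% to 25% of about 20 subjects per arm stopping early, which is 2 to 5 subjects. Each has one ETT panel, which enters at most one window. The four rows together then hold at most 2 to 5 ETT values per arm, an average of at most 0.5 to 1.25 per row, plus any unscheduled draws. This bound makes no assumption about when subjects stop.

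**The case against.** The strongest reply is that SAP 8.4.2 ties the main chemistry tables to scheduled time points, and by the SAP's own schedule Weeks 24 to 60 are not scheduled time points for creatinine or glucose. On that reading the rows are never printed. This largely stands for analytes other than CPK. The SAP does not say it by analyte, however, and Table 10-3 names those visits for all serum chemistry, so two programmers could produce different tables. It does not help for CPK, whose thresholds are requested by visit.

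A second reply is that nothing is hidden or lost. Safety analysis is descriptive without testing, n is a required statistic, CPK thresholds are also summarized over the treatment-emergent period, and all individual data are listed. That stands, and it limits the size of the point.

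Two stronger readings are tempting and are not supported:

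- **That about two thirds of ETT panels are misplaced, because the four windows cover 336 of 504 treatment days.** A share of days becomes a share of panels only under a stopping-time distribution that the documents do not give. Nor are the values misplaced in time: a Day 300 panel goes to Week 48 (Day 337), 37 days away. What is missing is continuing subjects to compare it with.
- **That a secondary safety endpoint is misstated whichever way the plan is read.** If the rows are suppressed, the fault is an unstated rule for where ETT values go. That is an ambiguity or an omission from by-visit tables. It does not make a reported result wrong.

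**Conclusion.** The mismatch is real. Table 10-3 conflicts with the SAP's own sampling schedule for non-LFT chemistry. If scheduled visits stay within tolerance, the Day 128 to 463 windows can hold only ETT and unscheduled values for those analytes. The conclusion is firm for the CPK by-visit threshold table. For the other analytes it depends on how a programmer reads the scheduled-time-point wording.

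The consequence is small: a few sparse, selected rows in descriptive by-visit tables that should not be compared between arms or with other visits. The primary endpoint, the listings and the treatment-emergent-period LFT and CPK summaries do not change. It is worth correcting before database lock because the rule is wrong on its face and the correction is nearly free.

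**What to change.** Split the serum chemistry entry in SAP Table 10-3 into two rows.

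- **LFTs** (ALT, AST, GGT, ALP, direct and total bilirubin, as in Protocol 11.6.3): keep the present windows.
- **Non-LFT chemistry, including CPK:** Baseline ≤1, Day 15 [2, 22], Week 4 [23, 57], Week 12 [58, 127] and Week 72 [464, 519], with no by-visit rows for Weeks 24 to 60.

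State in SAP 8.4.2 that the by-visit CPK threshold table follows the second row. State also that ETT and unscheduled non-LFT values from Days 128 to 463 enter the treatment-emergent-period maximum/minimum and threshold summaries and the listings. Section 8.4.2 currently names a treatment-emergent-period threshold summary only for LFTs and CPK. For analytes such as creatinine it should therefore say that the Appendix H criteria are applied over that period; otherwise their mid-study ETT values would reach only the listings.

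Stretching the neighboring windows by the midpoint rule is not recommended. (85 + 505)/2 = 295 would give Week 12 [58, 295] and Week 72 [296, 519]. A Day 300 ETT value would then be labeled Week 72, 505 − 300 = 205 days from target, and a Day 295 value Week 12, 295 − 85 = 210 days from target. Both would be mixed with on-schedule subjects, where n no longer reveals them.

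The cost is one added table row, a sentence or two in 8.4.2 and minor programming. The downside is that mid-study ETT and unscheduled non-LFT values no longer appear in the by-visit tables.
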